4.0 Study Objectives and End Points

Primary Objective:

- 1- To decrease the rate of progression to hypoxemic respiratory failure in high risk patients with Covid-19, treated with prophylactic steroids during the first phase of the disease.
 - a. Hypoxemic respiratory failure is defined as:
 - 1. O_2 saturation of < 91% or pO_2 <60 on room air
- 2- To evaluate the rate of complications of patients observed without treatment.
 Complications include progression to respiratory failure or any other complication leading to hospitalization.

Secondary Objectives:

- 1. To determine % survival at 28 days from registration on this clinical trial
- 2. To determine if there is any improvement in inflammatory markers following treatment with corticosteroids.
- 3. To define the length of hospitalization
- 4. To determine the frequency of admissions to ICU.
- 5. To determine the percentage of patients who require ventilatory support.
- 6. To determine the rate of complications and progression to respiratory failure in patients with favorable features (i.e., those eligible for observation and not for therapy with methylprednisolone.)
 - a. To validate these results in an independent cohort of cases diagnosed as Covid-19 from our general hospital population.
- 7. We will evaluate the proportion of patients with clinical improvement, as defined by live discharge from the hospital, a decrease of at least 2 points from baseline on a modified ordinal scale (as recommended by the WHO R&D Blueprint Group), or both. [10]
 - 7.1 The six-point scale consists of the following categories:
 - (1) not hospitalized;

- (2) hospitalized, not requiring supplemental oxygen;
- (3) hospitalized, requiring supplemental oxygen;
- (4) hospitalized, requiring nasal high-flow oxygen therapy, noninvasive mechanical ventilation, or both;
- (5) hospitalized, requiring invasive mechanical ventilation, ECMO, or both; and
- (6) death.

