6.0 Inclusion Criteria

- 6.1 All patients diagnosed with Covid-19 will be registered on the study regardless of their severity, but only those who meet high risk criteria will be treated with steroids. Those who do not meet the criteria will only be registered with no need to collect further data except baseline labs and CT chest. They should sign the consent form and the data manager can collect the rest of the information.
- 6.2 Male or female patients of 21 years or older diagnosed with Covid-19 by PCR or by rapid serological test will be eligible. Diagnosis of Covid-19 will be established by means of either the PCR molecular test or with the rapid serologic test or both. (see figure 3)

We have learned recently that some cases produce IgG very early and presence of IgG doesn't mean that infection is late. Those who are IgM positive but PCR negative, will be considered as "suspicious for Covid-19"; however, if their clinical presentation is typical for Covid-19, (see below) they will be counted as a positive diagnosis. Those who are IgM positive but PCR negative, for purposes of analysis will be divided as "polysymptomatic" (2 or more symptoms characteristic of Covid-19) or "not polysymptomatic". The symptoms considered as characteristic are fever, cough, dyspnea, myalgia, diarrhea, anosmia/dysgeusia, malaise, headache, abdominal pain, neurological symptoms (paresthesiae, delirium etc).

- 6.2 a. Patients who have negative Covid IgG and IgM but whose PCR results are not available yet and who have typical symptoms of Covid-19 (see section 6.2 above), or who have typical CT chest findings such as ground glass opacities, will be considered eligible. If PCR later on turns to be negative, the patient will be retrospectively considered as ineligible.
- 6.3 Eligible patients will be registered on study on or before 10 days from first onset of symptoms. Patients whose symptoms started > 10 days ago; but who are not in respiratory failure are eligible if they are still symptomatic.
- 6.4 In order to be treated with methylprednisolone, they must meet at least two of the following criteria on or shortly before day 10 (but not before day 7)

 from first onset of symptoms, in order to avoid treatment during viral phase; if two criteria are met before day 7, patient is eligible but treatment should not start before day 7 of illness:
 - 6.4.1 Serum IL-6 \geq 10 pg/ml before day 10.
 - 6.4.2 Ferritin> 500 ng/ml before day 10.

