 - 6.4.3 D-dimer > 1 mg/L (1,000 ng/ml) before day 10.
 - 6.4.4 CRP > 10 mg/dL (100 mg/L) before day 10.
 - 6.4.5 LDH above normal before day 10.

- 6.4.6 Lymphopenia (absolute lymphocyte count <900) before day 10.
- 6.4.7 O₂ saturation <94% by pulse oximetry, but more than 91%, before day 10.
- 6.4.8 CT chest with evidence of infiltrate(s).
- 6.5 Interpretation of results of rapid and PCR molecular tests:
 - 6.5.1 Those with serological positive test but negative molecular PCR test will be analyzed based on the clinical context. See below.
 - 6.5.2 Those who present with at least 2 of the following typical symptoms of Covid-19 (cough, fever, dyspnea, diarrhea, anosmia) will be considered as likely cases of Covid-19 while those with one or less symptoms will be considered as unlikely cases but will still be considered evaluable. They will be analyzed separately.
 - 6.5.3 Those who are PCR positive and serology positive or negative will be considered as definitive cases.
- 6.6 The CALL score will be used in the analysis of all cases (11). This score represents a composite index based on presence of comorbidities, age >60, lymphopenia and elevated LDH. Those cases with a score >6 have greater than 50% risk for serious complications.
- 6.7 Simultaneous treatment will be allowed with the following drugs: remdesivir, hydroxychloroquine, azithromycin, vitamin C, doxycycline, colchicine, zinc and ivermectin. Patients who have received 1 single dose of dexamethasone or methylprednisolone will be eligible. **Their use is not considered as a basis for exclusion** from this trial.

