7.0 Exclusion Criteria

- 7.1 Any patient with life expectancy <1 month
- 7.2 Any patient who is oxygen dependent
- 7.3 Any patient with long standing history of severe COPD

- 7.4 Any patient who is chronically oxygen dependent because of previously existing lung disease
- 7.5 Anyone with severely uncontrolled diabetes despite adequate management.
- 7.6 Anyone with active serious bacterial infection such as septicemia or pneumonia.
- 7.7 Anyone receiving Tocilizumab (anti-IL-6 therapy) or plasma therapy
- 7.8 Any patient already receiving steroids for another pre-existing illness
- 7.9 Cases who are IgG positive but IgM negative, will not be considered eligible unless they are positive by molecular PCR test or symptoms are highly suggestive of Covid-19 (> 3 of the following: cough, dyspnea, anosmia, diarrhea, myalgia, ground glass infiltrate(s) in CT chest) within first 10 days of illness.

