10.0 Primary Response Criteria for patients receiving methylprednisolone

10.0.1 Clinical complete response criteria require all the following:

10.0.1.1	No need for ventilatory support at any point
10.0.1.2	Not oxygen dependent by day 28 of registration
10.0.1.3	Alive by day 28 from registration on trial
10.0.1.4	CT chest with minimal or no evidence of disease by day 28
	from registration

10.0.2 Clinical partial response criteria require that 2 of the following be present by day 14 of therapy:

10.0.2.1	No need for ventilatory support at any point
10.0.2.2	Not oxygen dependent by day 28 from registration on trial
10.0.2.3	CT chest stable to improve over baseline by day 28 from
	registration

10.1 Secondary Response Criteria:

- 10.1.1 Decrease of at least 25% in anyone of the following markers, if elevated at baseline: IL-6, ferritin, D-dimer, CRP or LDH by day 14
- 10.1.2 Improvement of absolute lymphocyte count in those presenting with lymphopenia. Improvement is defined as increase by 25 % or more by day 14.

11 Data Management

- 11.1 Patients will be registered after obtaining signed consent form.
- 11.2 Registration will be performed at Auxilio Mutuo by calling [contact] [name].

12 Statistical Analysis

- 12.0 Analysis will focus in comparing pre-treatment and post treatment values.

 Results will be analyzed using the intent to treat principle which in this case means that those cases who receive at least one dose of methylprednisolone will be considered evaluable.
- **12.1** Evaluable cases are considered as those who have clinical data for at least 1 subsequent day.
- 12.2 Due to the small sample size, non-parametric tests for matched data will be used.

13.0 REFERENCES:

- 1. Gautret, P., et al., *Hydroxychloroquine and azithromycin as a treatment of COVID-19:* results of an open-label non-randomized clinical trial. Int J Antimicrob Agents, 2020: p. 105949.
- 2. Chen, L., et al., *Convalescent plasma as a potential therapy for COVID-19.* Lancet Infect Dis, 2020. **20**(4): p. 398-400.
- 3. Carr, A.C., A new clinical trial to test high-dose vitamin C in patients with COVID-19. Crit Care, 2020. **24**(1): p. 133.
- 4. Zhou, F., et al., Clinical course and risk factors for mortality of adult inpatients with COVID-19 in Wuhan, China: a retrospective cohort study. Lancet, 2020. **395**(10229): p. 1054-1062.

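### Protocol 6.7 admits patients with one prior steroid dose of unstated timing, so a marker baseline can be post-steroid and the cohort observed without treatment can include steroid-exposed patients

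*Protocol*

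**What the plan says.** - **Prior steroid.** Protocol 6.7 lists permitted concurrent drugs and then adds: "Patients who have received 1 single dose of dexamethasone or methylprednisolone will be eligible". It goes on: "Their use is not considered as a basis for exclusion". No dose size, illness day or order relative to blood sampling is given, and the permission is for the trial as a whole, not one group.
- **Exclusion.** The only steroid exclusion, 7.8, is "Any patient already receiving steroids for another pre-existing illness".
- **Allocation.** Under 6.1 all diagnosed patients are registered, but "only those who meet high risk criteria will be treated with steroids". For the rest: "Those who do not meet the criteria will only be registered with no need to collect further data except baseline labs and CT chest". Section 6.4 requires at least two of eight criteria: IL-6, ferritin, D-dimer, CRP, LDH, lymphocyte count, oxygen saturation and CT infiltrate. It delays study treatment to day 7 of illness "in order to avoid treatment during viral phase".
- **Baseline sampling.** Section 2.1 places the labs at or before entry. Only the CT is timed against methylprednisolone, and only as a preference.
- **Use of the baseline.** Section 10.1.1 scores this marker response: "Decrease of at least 25% in anyone of the following markers, if elevated at baseline". Section 12.0 bases the analysis on pre-treatment against post-treatment values, and calls evaluable anyone who has had one or more doses of methylprednisolone.
- **Observed cohort.** Primary Objective 2 is "To evaluate the rate of complications of patients observed without treatment".

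**The concern.** The trial's marker analysis needs a value taken before steroid exposure, and one of its two primary objectives needs a group that was not given the treatment under study. Section 6.7 lets in patients for whom neither need be true, and no section separates or flags them.

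The observed cohort matters beyond its own rate. Section 3.0 says the low-risk data are meant to guide which patients can be managed as outpatients or discharged. A complication rate that partly reflects patients given a steroid before entry is not the rate for patients managed with none.

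**Working it through.** The protocol states no derived figure on this point, so there is nothing to reproduce. The check sets the sections side by side; the arithmetic afterwards is for scale only.

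**Step 1: can a pre-dosed patient enter?** Yes. Section 6.7 admits one dose of either named drug. Section 7.8 covers only steroids for another pre-existing illness, so a dose given for Covid-19 falls outside it.

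**Step 2: can the baseline be post-steroid?** Yes. Section 2.1 sets the labs relative to entry, not relative to any earlier steroid. A dose followed by entry labs satisfies every rule. A baseline may also predate the dose, but nothing requires it.

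**Step 3: where does the patient go?** With two or more 6.4 criteria, to methylprednisolone. With fewer, 6.1 registers the patient without study treatment, which is the cohort of Primary Objective 2. Neither section asks about prior steroid.

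**Step 4: evaluability.** Section 12.0 does not say whether a dose before registration counts. Read literally, an observed patient with one earlier dose of methylprednisolone meets the evaluability rule for the treated analysis.

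**Scale of the marker effect.** Let f be the fraction by which the prior dose has lowered a marker (assumed; not in the protocol). A 25% fall from the post-dose baseline equals a total fall from the pre-dose level of 1 − (1 − f) × 0.75. A pre-dose value up to cut-off/(1 − f) can read at or below the cut-off.

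| f (assumed) | Total fall needed for response | Pre-dose CRP that can read ≤ 100 mg/L | Pre-dose ferritin that can read ≤ 500 ng/ml |
|---|---|---|---|
| 10% | 32.5% | up to 111 | up to 556 |
| 20% | 40% | up to 125 | up to 625 |
| 30% | 47.5% | up to 143 | up to 714 |
| 50% | 62.5% | up to 200 | up to 1000 |

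**Scale in the observed cohort.** Section 5.2 is read as 100 to 200 registered, with 40 to 60 eligible for methylprednisolone. The observed group is then between 100 − 60 = 40 and 200 − 40 = 160. For an assumed pre-dosed share q:

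- q = 5%: 2 to 8 patients
- q = 10%: 4 to 16 patients
- q = 20%: 8 to 32 patients

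If never-dosed patients have complication rate p and pre-dosed patients have relative risk r, the observed rate is p(1 − q) + p·r·q. With p = 10% and q = 20% (both assumed), r = 0.5 gives 8% + 1% = 9%, and r = 1.5 gives 8% + 3% = 11%. With q = 5% the same values of r give 9.75% and 10.25%.

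**The case against.** **The day-7 rule.** A reader might infer that 6.7 contradicts 6.4, because a dose in the viral phase is accepted while 6.4 is written to avoid one. The text does not support a strict contradiction: 6.4 governs when study treatment starts, and 6.7 concerns a dose given before the trial had any control. What remains is that the protocol does not say how the two fit together.

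**Meaning of untreated.** Secondary Objective 6 describes the observed group as those not eligible for methylprednisolone therapy, so the label may mean no study therapy. Section 6.7 also permits remdesivir, colchicine and other drugs, so the cohort was never drug-free. This is fair, but a dose of the study drug or another corticosteroid differs from other background care, because it is the intervention whose absence defines the cohort.

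**Patients switching groups.** A reader might infer that high-risk patients will be moved into observation. With an assumed 25% fall, CRP of 12 mg/dL becomes 12 × 0.75 = 9 and ferritin of 600 becomes 600 × 0.75 = 450 ng/ml, both below their cut-offs. But 25% is a response threshold at day 14, not an estimate for one dose. If both markers fall below their cut-offs, the patient switches only if at most one of the other six criteria is met, and one who meets none must have no CT infiltrate either. A pre-dose lab can also already count, since 6.4 accepts criteria met before day 7. Misallocation is possible but not shown.

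**A matter for the SAP.** Baseline definitions and sensitivity analyses often belong there, and the SAP is not shown. But eligibility, lab timing and the cohort are fixed in this protocol, and no analysis can use the date of a prior dose unless it was recorded. No section requires that.

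**Conclusion.** The point holds in a limited form. As written, the plan can give 10.1.1 and 12.0 a baseline that is not pre-treatment, and can count steroid-exposed patients in the cohort of Primary Objective 2. The 6.4 allocation can also rest on post-steroid markers.

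The size of the bias cannot be determined, because the share of pre-dosed patients and the effect of one dose are not given. The ranges above rest on assumed values of f, q, p and r.

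A reader might infer that the marker results would flatter the drug. On the premise that steroids lower these markers, the reverse holds: a lowered baseline makes the 25% fall harder to reach, and this is a secondary criterion. Nor do the respiratory-failure definition in 4.0 and the 50% success rule in 5.4 use marker baselines. They can be affected only through which patients are in the treated group and what they had received before.

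This is a worthwhile, inexpensive correction to an exploratory pilot, not a flaw that undermines it.

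**What to change.** 1. Record the drug and date of any steroid dose before registration, for every registered patient.
2. For 10.1 and 12.0, take as baseline the labs drawn before that dose. Where none exist, leave the patient out of the marker-response analysis.
3. Analyse the Primary Objective 2 cohort without pre-dosed patients, and report those patients separately.
4. Report the treated group's respiratory-failure rate with and without pre-dosed patients.
5. State in 12.0 whether a dose before registration counts towards evaluability.
6. The sponsor must reconcile 6.7 with 6.4, both on the day-7 rule and on the timing of the criteria relative to a prior dose. No clinical rule is proposed here.

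The cost is a few sentences, one extra item of data per patient and one sensitivity analysis. The downside is slightly fewer patients in the marker and observed-cohort analyses.

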7.0 Exclusion Criteria

- 7.1 Any patient with life expectancy <1 month
- 7.2 Any patient who is oxygen dependent
- 7.3 Any patient with long standing history of severe COPD

- 7.4 Any patient who is chronically oxygen dependent because of previously existing lung disease
- 7.5 Anyone with severely uncontrolled diabetes despite adequate management.
- 7.6 Anyone with active serious bacterial infection such as septicemia or pneumonia.
- 7.7 Anyone receiving Tocilizumab (anti-IL-6 therapy) or plasma therapy
- 7.8 Any patient already receiving steroids for another pre-existing illness
- 7.9 Cases who are IgG positive but IgM negative, will not be considered eligible unless they are positive by molecular PCR test or symptoms are highly suggestive of Covid-19 (> 3 of the following: cough, dyspnea, anosmia, diarrhea, myalgia, ground glass infiltrate(s) in CT chest) within first 10 days of illness.

8.0 Management and Dosing Regimen

- 8.1 Patients will be admitted to a regular room in the hospital (**not** ICU)
- 8.2 They will be monitored closely with vital signs every 8 hours to ensure their respiratory and cardiovascular status do not deteriorate.
- 8.3 Methylprednisolone 80 mg IV bolus injection will be given daily x 5 days starting upon day 1-3 of registration on trial. Patients who are stable with O2 sat >94% and no other indication for hospitalization will be treated as outpatient with methylprednisolone 80 mg p.o. x 5 days.

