2.0 Schedule of Study Assessments

- 2.1 At, or prior to, entry into study:
 - 2.1.1 History and Physical exam
 - 2.1.2 Labs: CBC, CMP, LDH, arterial blood gases, serum IL-6, serum ferritin, CRP, D-dimers, troponin
 - 2.1.3 Radiologic studies: CT chest without IV contrast preferably prior to treatment with methylprednisolone.
 - 2.1.4 Other studies:
 - 2.1.4.1 Either PCR for molecular detection of SARS-Cov-2 virus and serologic rapid test (IgG, IgM), or both (see figure 2). Cases who are IgG positive but IgM negative, will not be considered eligible unless they are positive by molecular PCR test or they are acutely ill with symptoms typical of Covid-19 (see section 6.2 for typical symptoms).
 - 2.1.4.2 O₂ saturation by pulse oximetry
 - 2.1.4.3 Influenza rapid test if considered necessary.
- 2.2 During study (only applies to those eligible for treatment with methylprednisolone):
 - 2.2.1 For patients admitted to hospital: Vital signs q 8 hours (not q 4 hrs) to reduce chance of nursing staff contamination
 - 2.2.2 Day 7-10 from first symptom of illness: CBC, CMP, LDH, serum IL-6, serum ferritin, CRP, d-dimers
 - 2.2.3 Day 14 from registration on trial:

- 2.2.3.1 repeat CBC, CMP, LDH, serum IL-6, serum ferritin, CRP, d-dimers
- 2.2.3.2 repeat PCR for molecular detection of SARS-Cov-2 virus
- 2.2.4 Day 28 from registration on trial:
 - 2.2.4.1 repeat CBC, CMP, LDH, serum IL-6, serum ferritin, CRP, d-dimers
 - 2.2.4.2 repeat PCR for molecular detection of SARS-Cov-2 virus
 - 2.2.4.3 CT chest without IV contrast

[figure not shown]

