Usually anti-inflammatory therapy with an anti-IL-6 antibody, Tocilizumab, is reserved for patients who are evolving poorly, especially patients with severe pneumonia with elevated IL-6 serum levels [6]. However, once these patients have pneumonia, anti-inflammatory treatment is usually not very successful. Nevertheless, the use of methylprednisolone has been associated with substantial reduction of risk of death even if administered late, when patients already have ARDS[7]. However, if given late, the probability of dying is 52%[7].

[name], from Hospital Peset, in Valencia, Spain has developed an approach designed to anticipate the second, or so-called inflammatory phase. He has proposed that when the pulmonary infiltrates appear, this is no longer an infectious process, but it is purely an inflammatory or immune issue which causes anatomical injury to the capillary alveolar membrane resulting in respiratory distress. He uses corticosteroid therapy starting on the sixth day of the onset of symptoms, given for 5-7 days, with the goal of preventing the inflammatory phase. Steroids are used specifically to treat those cases who on day 6 are febrile and show elevation of serologic inflammatory markers without advanced radiologic pulmonary manifestations. His initial results reportedly are excellent and admissions to the intensive care unit decreased, with shortened hospital stays and radiological and favorable clinical evolution that he has described as "spectacular" (personal communication)

In Spain and Italy this approach is gaining acceptance but at present time it is not considered standard of care. The use of steroids has been criticized because there is no evidence from randomized clinical trials to support its use for COVID-19. In addition, the anti-inflammatory medications, may delay the elimination of virus and increase the risk of secondary infection.

However, there is no evidence that, as proposed by [name], a short course of steroids given shortly before the second phase of the disease to patients at high risk of entering the inflammatory phase, has had any unfavorable impact on the disease. Thus, the concern against its use is totally based on theoretical grounds. The few data available against the use of steroids come from trials in which they have used them either too late or too early[8].

[figure not shown]

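### Section 8.3 times the first IV dose from registration and section 6.4 from symptom onset, so a patient registered on illness days 1–4 has no start day that meets both

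*Protocol*

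**What the plan says.** Two sections of the protocol fix the start of methylprednisolone, each on its own clock.

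- **Section 8.3 (registration clock).** "Methylprednisolone 80 mg IV bolus injection will be given daily x 5 days starting upon day 1-3 of registration on trial". Nothing in this sentence refers to illness day or to section 6.4. The next sentence of 8.3 gives the outpatient alternative: stable patients "will be treated as outpatient with methylprednisolone 80 mg p.o. x 5 days".
- **Section 6.4 (symptom clock).** A patient needs at least two of the listed risk criteria. To keep steroids out of the viral phase, the section adds: "if two criteria are met before day 7, patient is eligible but treatment should not start before day 7 of illness".

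Three other places bear on how early a patient can be registered.

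- **Section 6.1:** "All patients diagnosed with Covid-19 will be registered on the study regardless of their severity".
- **Section 6.3:** "Eligible patients will be registered on study on or before 10 days from first onset of symptoms". This sets a latest day (with an allowance for patients still symptomatic after it) but no earliest one.
- **Section 2.2.2:** among the assessments made during the study for patients eligible for methylprednisolone, labs are scheduled at "Day 7-10 from first symptom of illness". That fits patients who are already on study before illness day 7.

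The protocol does not say which start rule takes precedence.

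**The concern.** The two clocks agree only when registration falls late enough in the illness. For an eligible patient registered early, the three days allowed by 8.3 can all pass before 6.4 permits a first dose. Section 6.4 describes this patient and calls the patient eligible, so the protocol foresees the case.

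Start timing is the core of the treatment hypothesis. The primary objective in section 4.0 concerns steroids given in the first phase of the disease. Section 3.0 says the few unfavourable steroid data "come from trials in which they have used them either too late or too early". Treating staff are most likely to look for the start day in the dosing section, and for these patients that section alone gives the wrong answer.

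**Working it through.** **Inputs**

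- IV start window: day 1 to day 3 of registration (8.3).
- Earliest permitted start: illness day 7 (6.4).
- Registration: any illness day up to day 10, with no lower limit (6.1, 6.3).
- Course length: 5 daily doses (8.3).
- Follow-up labs: "Day 14 from registration on trial" (2.2.3).

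The protocol does not say whether the day of registration is day 0 or day 1, so both are shown. The first day of symptoms is taken as illness day 1. If it were day 0, that day would join the affected range.

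**Step 1. Put both rules on the illness clock.** Let r be the illness day of registration.

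- Registration = day 1: the 8.3 window is illness days r to r+2.
- Registration = day 0: the window is illness days r+1 to r+3.

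Both rules can be met only if the last day of the window is illness day 7 or later.

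- Registration = day 1: r+2 ≥ 7, so r ≥ 5.
- Registration = day 0: r+3 ≥ 7, so r ≥ 4.

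**Step 2. Count the days in the window that comply with 6.4.**

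| Illness day at registration (r) | Window, registration = day 1 | Complying days | Window, registration = day 0 | Complying days |
|---|---|---|---|---|
| 1 | 1–3 | 0 of 3 | 2–4 | 0 of 3 |
| 2 | 2–4 | 0 of 3 | 3–5 | 0 of 3 |
| 3 | 3–5 | 0 of 3 | 4–6 | 0 of 3 |
| 4 | 4–6 | 0 of 3 | 5–7 | 1 of 3 |
| 5 | 5–7 | 1 of 3 | 6–8 | 2 of 3 |
| 6 | 6–8 | 2 of 3 | 7–9 | 3 of 3 |
| 7 | 7–9 | 3 of 3 | 8–10 | 3 of 3 |

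No common start day exists for r = 1–4 (registration = day 1) or r = 1–3 (registration = day 0). Only part of the window complies for r = 5–6 or r = 4–5 respectively.

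**Step 3. Test the remedy.** Suppose the first dose is due on registration day 1–3 or on illness day 7, whichever is later. Every value of r then has at least one permitted day, and none is before illness day 7.

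**Step 4. See what the delay does to the day-14 labs.** They stay on the registration clock and fall on illness day r+13 (registration = day 1) or r+14 (registration = day 0). The extreme case is r = 1 with a first dose on illness day 7.

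- Registration = day 1: labs on illness day 14, which is 14 − 7 = 7 days after the first dose.
- Registration = day 0: labs on illness day 15, which is 15 − 7 = 8 days after the first dose.
- The fifth dose is on illness day 7 + 4 = 11, so the labs follow the end of the course by 3 or 4 days.

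**The case against.** The strongest reply is that 6.4 already deals with this patient. It names the case, orders the delay and gives the reason, whereas 8.3 is a general dosing line. A specific, reasoned hold would ordinarily override a general window, which would leave only a missing cross-reference. Most of this stands. It makes early dosing unlikely and keeps the point small. It does not make 8.3 correct: read as written, that section gives these patients a start window they must not use, and nothing in it points to 6.4.

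A reader might infer more than this. The documents do not support the following readings.

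- **Patients will be dosed in the viral phase.** This would require staff to ignore an explicit instruction in 6.4.
- **Patients who first qualify on the illness-day 7–10 labs will miss the 8.3 window.** Section 2.2 limits those labs to patients already eligible for treatment, and 6.1 asks for no further data beyond baseline labs and CT from the others. No scheduled route leads to late qualification.
- **No latest start day remains once 6.4 overrides 8.3.** Section 6.4 requires the criteria to be met on or shortly before illness day 10, which in practice also bounds treatment, apart from the still-symptomatic patients admitted by 6.3.
- **Oral patients have no start day.** The oral sentence follows directly on the IV sentence and changes route and setting; the start day is naturally carried over. Saying so costs nothing, but its absence has no shown consequence.
- **The marker responses in 10.1 are distorted.** That section says only by day 14, without naming a clock, and no effect of a varying interval can be derived.

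**Conclusion.** The contradiction is real and confined to start timing. Patients registered on illness days 1–4 (1–3 if registration is day 0) cannot satisfy both sections, and those registered on days 5–6 (4–5) can use only part of the 8.3 window. This follows from the stated rules and the two day-numbering conventions, and it depends on no sample-size or power assumption. How many patients it touches cannot be computed, because the protocol gives no distribution of illness day at registration.

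Section 6.4 should govern. No harm to the primary objective is shown, and under 12.0 a patient who receives one dose is evaluable whatever the start day. Severity is minor. It is still worth correcting, because the sentence at fault is a dosing instruction on the very feature the trial sets out to test.

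**What to change.** Amend 8.3 so that the first dose is given on registration day 1 to 3 or on illness day 7, whichever is later, and never before illness day 7, with a cross-reference to 6.4. State that this applies to both IV and oral dosing. Record the illness day of the first dose for every treated patient.

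The cost is one sentence in 8.3 and one recorded item; no visit moves. The downside is a shorter gap between first dose and day-14 labs for patients registered early. At its shortest it is 7 days (8 if registration is day 0), which is still after the last of the five doses.
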